Obesity and overweight have become an important health burden in children and adolescents, with 19% of all children between 5 and 18 years being either obese or overweight in Belgium(1,2). Obesity and especially visceral adiposity early in life may contribute to the development of cardiovascular disease at older age, as it shows tracking into adulthood and is associated with cardiovascular risk

factors such as dyslipidemia, insulin resistance, arterial hypertension and low grade inflammation, in a variable percentage (4) (5)

Low grade inflammation, as assessed by hSCRP, was found to be present in 20.6 % and 19.8 % of overweight children and adolescents (6). In adults, hSCRP levels between 1 and 3 mg/L and above 3 mg/L are considered coronary disease risk factors (7).

Endothelial dysfunction, known to precede the formation of atherosclerotic plaque, can be assessed in a non-invasive manner in children by peripheral artery tonometry. (8) Only few studies have been performed in obese children with this bed-side technique, showing either normal or a disturbed function, reflected by a lower reactive hyperemia index (9, 10,11) The association with low grade inflammation however was assessed in only one study. We hypothesize that in adolescents and young adults with a history of childhood obesity a more disturbed endothelial function will be present in those with and /or current elevated hSCRP value.

Study Objectives

To investigate whether obese and overweight adolescents with an elevated hs-CRP are more at risk for the development of endothelial dysfunction assessed peripheral artery tonometry, compared to those with a normal hs-CRP at their initial evaluation for obesity-associated metabolic syndrome

To assess the degree of endothelial dysfunction, assessed by the reactive hyperemia index by peripheral artery tonometry in adolescents and young adults with a history of childhood obesity in relation to their current hs CRP value

To investigate the changes in hs-CRP and adiposity in adolescence and young adulthood of initially obese children and adolescents with either normal or elevated hs-CRP levels

Study outcomes

1. Primary outcome

Reactive hyperemia index (RHI) measured by the EndoPAT device

2. Secondary outcome

hs CRP value , BMI z-score and body fat percentage assessed by skinfold thickness

Study design

1. Overall design

This is an observational cohort study

2. Randomization/blinding procedure.

Not applicable.

3. Statistical methodology

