The statistical analysis will be done with the SPSS software.

The difference in THI index between the population with and without low grade inflammation will be evaluated by the Mann Whitney U test and Multivariate analysis of variance, taking current hCRP, age, BMI z-score, and systolic blood pressure into account. The change in hS

CRP in the population with and without low grade inflammation will be analyzed by the Kruskall Wallace test.

The power calculation was done at clincalc.com/stats/samplesize software. Assuming a mean RHI score of 1.51 in overweight children with a standard deviation of 0.2 (9), assuming an equal distribution between the study groups (elevated vs. normal hs-CRP), we have a power of 0.80 to demonstrate a difference of 20 % between the two groups with 27 patients enrolled in each group.

Study population

1. Recruitment

Eligible candidates will be recruited within the children with overweight and obesity having a metabolic risk evaluation before treatment in the period 2006 and 2010 at the pediatric clinic of the UZ Brussel. In total 60 participants will be investigated. Firstly, 30 participating patients with initially elevated hsCRP will be selected at random (following the date of their initial investigation) and afterwards matched for age, BMI z-score, and blood pressure with the same number of patients without initially elevated hCRP values

2. Recruitment procedure

Eligible candidates, or their parents if underage, will be personally contacted by telephone and/or e-mail by their initial pediatric endocrinologist and will be invited to partake in the study. All written information about the study will be provided beforehand.

3. Eligibility criteria

➤ Inclusion Criteria:

- Age 12-21 years at the moment of evaluation
- BMI > 1.3 SDS at the initial evaluation
- Hs-CRP available at initial evaluation

➤ Exclusion Criteria

- Acute or chronic Infection at the time of the study visit

Be or have been a smoker of tobacco

Study intervention

1. Study overview

A single visit is planned. During this visit a standard questionnaire on current health status, life style will be filled in a selfscore of pubertal development using standardized pictures will be done. Standard anthropometrics and blood-pressure measurements , a blooddrawn for hSCRP and a peripheral artery tonometry will be performed.

2. Identification of intervention

➤ Anthropometry:

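### The only adjusted RHI analysis conditions on current hs-CRP, so its group term need not equal the initial-hs-CRP contrast of the first objective

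*Combined protocol and SAP*

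**What the plan says.** All references are to the combined protocol and SAP.

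- **Study Objectives, first objective.** The exposure is hs-CRP at the start: adolescents with an elevated value are "compared to those with a normal hs-CRP at their initial evaluation for obesity-associated metabolic syndrome".
- **Study Objectives, second objective.** RHI is examined separately "in relation to their current hs CRP value".
- **Background and rationale.** The hypothesis mentions both values: a more disturbed function "will be present in those with and /or current elevated hSCRP value".
- **Study population, 1. Recruitment.** Thirty patients with initially elevated hs-CRP are chosen first, then "matched for age, BMI z-score, and blood pressure with the same number of patients without initially elevated hCRP values".
- **Study intervention, 1. Study overview.** At the single visit, "a blooddrawn for hSCRP and a peripheral artery tonometry will be performed". Current hs-CRP and RHI are therefore measured together, 5 to 10 years after the initial value according to the synopsis.
- **Study design, 3. Statistical methodology.** The RHI difference between groups is "evaluated by the Mann Whitney U test and Multivariate analysis of variance, taking current hCRP, age, BMI z-score, and systolic blood pressure into account".

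No adjusted RHI model without current hs-CRP is described. The analysis sentence does not say whether the groups are initial or current. It gives no time point for BMI z-score or systolic blood pressure, and it assigns no model to an objective.

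**The concern.** Current hs-CRP is measured after the exposure that defines the groups. It is also the exposure of the second objective and a secondary outcome. A model with both terms compares the initial groups at equal current hs-CRP. If initial inflammation is linked to RHI partly because it persists, that part is removed from the group term. If something unmeasured affects both current hs-CRP and RHI, the term can be biased in either direction. If neither holds, the term is unbiased but less precise.

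The title asks whether inflammation is an independent risk factor, and an adjusted model is a natural place to look for the answer. The plan has no rule for reading a weak adjusted term beside a clear Mann-Whitney difference. Initial inflammation could then be reported as not independently related to RHI, although the first objective asked only for the contrast by initial hs-CRP.

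**Working it through.** **Inputs from the protocol.** Statistical methodology gives the mean and SD ("Assuming a mean RHI score of 1.51 in overweight children with a standard deviation of 0.2") and the target ("a difference of 20 % between the two groups with 27 patients enrolled in each group"), with power 0.80. The synopsis gives α = 0.05. Recruitment gives 30 per group. Background gives about 20% of overweight children with low grade inflammation.

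**Assumptions (not in the documents).** *m* is the share of the group difference that runs through current hs-CRP. *r* is the correlation between initial and current log hs-CRP. The SD of 0.2 is taken as the total within-group SD. Tests are two-sided. Matching and the other covariates are not modelled.

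**1. The plan's own figure.** A 20% difference is 0.20 × 1.51 = 0.302.
- n per group = 2 × (1.960 + 0.842)² × 0.2² / 0.302² = 6.9, so 7, not 27.
- For 10% (0.151), the same formula gives 27.5, so 28.
- The difference that 27 per group detects with 80% power is 2.80 × 0.2 × √(2/27) = 0.152.

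The mismatch is a separate matter. It is why both 0.302 and 0.151 are used below.

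**2. Shift in the group term.** Initial log hs-CRP is taken as standard normal, cut at the 80th percentile, so the group means differ by 1.750. Current = r × initial + √(1 − r²) × noise. RHI = 1.51 − (1 − m) × D × group + b × current + error, with b = −m × D / (1.750 × r). The unadjusted difference is D and the adjusted group term is (1 − m) × D.
- m = 25%: 0.75 × 0.302 = 0.227
- m = 50%: 0.50 × 0.302 = 0.151
- m = 0: no shift. The standard error rises by about 5%, 12% or 26% for r = 0.3, 0.5 or 0.7.

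**3. Limit on m.** A total SD of 0.2 caps m at 0.2 × r × 1.750 / (0.302 × within-group SD of current). With within-group SDs of 0.973, 0.922 and 0.840, the cap is 36%, 63% or 97% for r = 0.3, 0.5 or 0.7.

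**4. Power of the adjusted group term** (simulated, 30 per group):

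| True difference | m | r = 0.3 | r = 0.5 | r = 0.7 |
|---|---|---|---|---|
| 0.302 | 0 | 100.0% | 99.9% | 99.5% |
| 0.302 | 25% | 100.0% | 98.6% | 94.2% |
| 0.302 | 50% | not attainable | 98.7% | 76.1% |
| 0.151 | 0 | 78.5% | 73.0% | 63.3% |
| 0.151 | 25% | 59.5% | 50.4% | 41.1% |
| 0.151 | 50% | 48.5% | 29.1% | 22.3% |

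Mann-Whitney power is at least 99% at 0.302 and about 80% at 0.151 throughout.

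**5. Shared cause, no mediation.** Take r = 0.5, an unmeasured factor with loading 0.3 or 0.5 on current log hs-CRP, and an effect of 0.1 per SD on RHI. The term moves by 0.1 × loading / 0.850 × 0.5 × 1.750, where 0.850 is the within-group variance of current hs-CRP. That is 0.031 or 0.051. A true 0.302 becomes 0.271 or 0.251 if the factor raises hs-CRP and lowers RHI, and 0.333 or 0.354 if it raises both. The factor would explain 0.1² / 0.2² = 25% of within-group RHI variance, so this is a strong case.

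**6. Which model suits the second objective.** The sample is selected 30:30 on initial hs-CRP. With D = 0.302 and no effect of current hs-CRP on RHI (m = 0), a model with current hs-CRP alone declares an association in about 23%, 52% or 84% of studies for r = 0.3, 0.5 or 0.7. The model that also contains initial group does so in about 5%.

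**The case against.** **The Mann-Whitney test already answers the first objective.** This stands if the groups are initial. That test omits current hs-CRP, and matching on age, BMI z-score and blood pressure gives some control of confounding. What it lacks is an adjusted estimate. A reader might infer that the first objective has no sound analysis, but the documents do not support that.

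**The groups might be current.** The wording leaves this open. Under that reading the Mann-Whitney test would also compare current groups, and the first objective would have no analysis. But recruitment forms the groups on initial values, so this reading is weak. A statement of the time point settles it.

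**A contrast at fixed current hs-CRP may be wanted.** Independence from current inflammation is a legitimate meaning of the title, and the hypothesis names current values. This is a reason to keep the joint model. It does not make that model's group term the first objective's contrast, and the plan states no such aim.

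**The harm is conditional and small at the planned effect.** This stands. Only one attainable cell at 0.302 falls below 94%. Shared causes are also limited by the exclusion of infection at the visit and of past or present smokers, and by the other covariates in the model.

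**Conclusion.** The point holds as a mismatch between the first objective and the only adjusted analysis. The group term equals the initial-hs-CRP contrast only under two conditions, no mediation through current hs-CRP and no unmeasured shared cause, which the documents neither state nor test. Under assumed mediation of 25% or 50%, 0.302 becomes about 0.227 or 0.151. Power mostly stays at 94% or more, with about 76% at r = 0.7 and 50% mediation. Large power losses need a smaller true difference, such as 0.151.

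A reader might infer that the adjusted model is certain to be biased, or that it would erase a real effect. The documents support neither: they give no tracking or mediation data, and under this model an SD of 0.2 rules out full mediation at 0.302 for r up to 0.7. The figures rest on the assumed m and r and on a cut at the 80th percentile. That cut uses a cited prevalence whose threshold is not given, whereas the synopsis uses 1 mg/L. The plan should be changed, but the unadjusted comparison of initial groups survives.

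**What to change.** 1. State that the RHI groups are defined by initial hs-CRP, and keep Mann-Whitney as the unadjusted comparison.
2. For the first objective, add a linear model or ANCOVA of RHI on initial hs-CRP group, without current hs-CRP. Adjust for age (with its time point stated) and for BMI z-score and systolic blood pressure from the initial evaluation. Rest any statement about the overall association of initial inflammation with RHI on this model and the Mann-Whitney test.
3. Keep the planned model with initial group and current hs-CRP, and give its covariates a time point. Use its current hs-CRP term for the second objective. Leaving initial group out would let it confound that term, as step 6 of the working shows. Read the group term only as an association not explained by current hs-CRP, and state the assumption of no unmeasured common cause.

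The cost is some wording and one extra model, with no new visits or patients. Initial BMI z-score and blood pressure must be taken from the file. Initial BMI SDS should be there, because eligibility requires it. Initial blood pressure should be confirmed: matching uses blood pressure, but its time point is not stated.

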Protocol Clinical Trial

Study synopsis

Study overview	
Title of clinical trial	Low grade inflammation in childhood obesity : an independent risk factor for endothelial dysfunction ?
Sponsor name	University Hospital of Brussels
Principal Investigator	prof. dr. [name] / [name]
Medical condition or disease under investigation	Obesity and overweight, cardiovascular risk factors
Purpose of clinical trial	To assess whether low grade inflammation in childhood obesity contributes to endothelial dysfunction
Primary objective	To investigate if the reactive hyperemia index by peripheral arterial tonometry is higher in adolescents with a history of childhood obesity and presenting a low grade inflammation in comparison with those without low grade inflammation (hSCRP < or > 1 mg/L)
Secondary objective (s)	To analyze the changes in hCRP and adiposity in obese children and adolescents after 5 to 10 years
Trial Design	Observational cohort study
Endpoints	RH-PAT scores, measured by peripheral artery tonometry . hSCRP, measured by automated immunoturbidometry BMI z-score and % body fat by skinfold thickness
Sample Size	54 (α= 0,05 – power 80%)
Summary of eligibility criteria	Overweight and obese adolescents, aged 12 to 21 years, with a known level of hs-CRP at initial evaluation for metabolic syndrome
Maximum duration of intervention	Single visit
Version and date of final protocol	Protocol version 1, date 18/08/2018
Version and date of protocol amendments	Not applicable

Study Schedule

Administrative information

1. Sponsor

The study is sponsored by the division of pediatric endocrinology of the University Hospital of Brussels (UZ Brussel).

2. (Principal) Investigator(s)

Prof. dr. [name]

Dr. [name]

[name]. [name]

[name] [name]

[name]

3. Departments involved

Department of Pediatrics

Division of Pediatric Endocrinology

University Hospital of Brussels

[name]

Ethical and regulatory information

1. Study registration

The study is registered at ClinicalTrials.gov and has a unique number: ####.

2. Study type

The study is an observational cohort study

3. Competent Ethics Committee

Central Ethics Committee:

Ethical Committee University Hospital of Brussels

[contact]

Email: [contact]

4. Ethical conduct of the study

The trial will be conducted in compliance with the principles of the Declaration of Helsinki (current version), the principles of Good Clinical Practice (GCP) and in accordance with all

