Anthropometric measurement sites are defined according to the international standards. (10)

- Weight will be measured using a calibrated digital scale (SECA, Hamburg, Germany) and will be rounded up to the nearest 0,05 kg. Participants will be wearing light clothing (underwear).
- Standing height will be measured using a stadiometer with a movable headboard and vertical backboard and will be rounded up to the nearest 0,1 cm.
- Waist circumference will be measured in the middle of the lowest rib (10th rib) and the iliac crest at the end of a normal expiration. The girths will be measured with a flexible Lufkin steel anthropometric tape (Lufkin W606PM).
- Tricipital and subscapular skinfold thickness will be measured by a Harpenden caliper using the Slaughter guidelines.
- The BMI z-score will be calculated using the Vlaamse groeistudie 2004 references
- The Slaughter formula will be used to calculate the body fat percentage.

➤ Blood pressure (mean of 3 measurements)

Blood pressure will be measured using an oscillometric, electronic device (Mindray). The blood pressure will be measured 3 times; the first measurement will not be taken into account and the mean of the second and third measurement will be calculated.

➤ Peripheral arterial tonometry

The pulse wave amplitude will be measured by a commercial finger plethysmograph EndoPAT, Itamar Medical Ltd, Caesarea, Isreal.)

Briefly explained, both index fingers of the patient are placed in the pneumatic probes. First the device performs 5 minutes of baseline measurement and thereafter a blood pressure cuff occludes the arterial flow of the arm for 5 minutes. After a rapid deflation of the cuff a

reactive hyperemia takes place which is a measure for the arterial endothelial function. There is a concomitant software package which calculates the Reactive Hyperemia Index (RHI) and peak dilatation.

Participants will be asked not to engage in strenuous sport activities the 24 hours preceding the test. (12)

hS-CRP

Will be measured at the Chemical Chemistry Laboratory of the UZ Brussel using by immunoturbimetry by the Vitros 4600 / Ortho Clinical Diagnostics analyzer.

Safety

1. Insurance

All damage or injuries resulting from the study participation will be covered by the no fault insurance available at Ethias through the University Hospital of Brussels.

2. Anticipated possible adverse events

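### The RHI analysis controls adiposity only through BMI z-score, so part of an hs-CRP association, mainly with current hs-CRP, may reflect abdominal fat that the study measures but does not use

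*Combined protocol and SAP*

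**What the plan says.** - **Question.** The title asks about "Low grade inflammation in childhood obesity : an independent risk factor for endothelial dysfunction". The claim at stake is independence, and adiposity is the obvious rival explanation.
- **Rationale** (Background and rationale). "Obesity and especially visceral adiposity early in life may contribute to the development of cardiovascular disease at older age". The same sentence ties this adiposity to "factors such as dyslipidemia, insulin resistance, arterial hypertension and low grade inflammation, in a variable percentage". By the protocol's own account, visceral fat is related both to the exposure (inflammation) and to the disease process that RHI stands for.
- **Objectives** (Study Objectives). The first compares RHI by hs-CRP at the initial evaluation. The second relates RHI to current hs-CRP.
- **Matching** (Study population, Recruitment). Patients with initially elevated hs-CRP are selected and "afterwards matched for age, BMI z-score, and blood pressure with the same number of patients without initially elevated hCRP values".
- **Model** (Study design, Statistical methodology). A Mann-Whitney test, and a multivariate analysis of variance "taking current hCRP, age, BMI z-score, and systolic blood pressure into account". The section does not say whether BMI z-score is the initial or the current value. No separate analysis is given for the second objective, so the current hs-CRP term in this model is the only one that bears on it.
- **Measurements** (Study intervention, Anthropometry). "Waist circumference will be measured in the middle of the lowest rib (10th rib) and the iliac crest". Height and two skinfolds are also taken. The secondary outcomes are "hs CRP value , BMI z-score and body fat percentage assessed by skinfold thickness". Waist appears in no outcome, matching rule or model, and body fat percentage is not a covariate.

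**The concern.** BMI is built from weight and height and carries no information on where fat lies. Two patients matched on BMI z-score can differ in abdominal fat. If abdominal fat raises hs-CRP and lowers RHI, hs-CRP and RHI will be associated at equal BMI z-score even if inflammation has no effect of its own. The planned analysis could not separate the two explanations, although the variable needed to try is collected.

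The two hs-CRP terms in the model are exposed differently. Initial hs-CRP defines the groups. Current hs-CRP is a covariate in the same model and takes up much of the abdominal-fat signal, because it is measured at the same visit as waist and RHI. The bias therefore falls mainly on the current hs-CRP coefficient and less on the group difference.

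**Working it through.** **Inputs from the plan.** RHI mean 1.51, SD 0.2, design difference 20%, 60 participants to be investigated (30 per group). The design difference is 0.20 × 1.51 = 0.302. The stated 27 per group does not follow from these inputs: 2 × (1.96 + 0.84)² × 0.2² / 0.302² = 6.9, so 7 per group (two-sided, normal approximation). That is a separate matter; 0.302 serves here only as a yardstick.

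**Assumed inputs.** The documents give none of these.
- r, correlation with RHI of the part of waist not explained by BMI z-score: -0.3 or -0.4.
- ρ, its correlation with current hs-CRP: 0.4 or 0.5.
- g, the gap between initial hs-CRP groups in that part of waist: 0.3, 0.5 or 0.8 SD.
- c, the gap in current hs-CRP between groups beyond what waist explains: 0.3 SD (with ρ = 0.4) or 0.5 SD (with ρ = 0.5).
- No true hs-CRP effect, linear relations, a two-sided 5% test (the plan does not state sidedness).

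**Step 1: current hs-CRP coefficient in the planned model.** Expected false slope per SD of hs-CRP = r × ρ × 0.2. Residual df = 60 - 6 = 54, so the standard error is about 0.2/√54 = 0.0272. Rejection probability ≈ Φ(|slope|/0.0272 - 1.96).

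| r | ρ | slope | slope/SE | rejection |
|---|---|---|---|---|
| -0.3 | 0.4 | -0.024 | 0.88 | 14% |
| -0.3 | 0.5 | -0.030 | 1.10 | 20% |
| -0.4 | 0.4 | -0.032 | 1.18 | 22% |
| -0.4 | 0.5 | -0.040 | 1.47 | 31% |

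Simulating the full model gives about 14-20% at r = -0.3 and 20-33% at r = -0.4. The result does not depend on g.

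**Step 2: initial hs-CRP group term.** If current hs-CRP were left out, the bias would be r × 0.2 × g: at r = -0.3, -0.018 / -0.030 / -0.048 for the three gaps, with simulated rejection of about 6% / 9% / 14%. The plan includes current hs-CRP, and the bias becomes r × 0.2 × [g(1 - ρ²) - ρc].

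| r | ρ, c | bias at g = 0.3 / 0.5 / 0.8 | simulated rejection |
|---|---|---|---|
| -0.3 | 0.5, 0.5 | +0.002 / -0.008 / -0.021 | 5% / 5% / 6% |
| -0.3 | 0.4, 0.3 | -0.008 / -0.018 / -0.033 | 5% / 6% / 8% |
| -0.4 | 0.5, 0.5 | +0.002 / -0.010 / -0.028 | 5% / 5% / 7% |
| -0.4 | 0.4, 0.3 | -0.011 / -0.024 / -0.044 | 5% / 7% / 12-13% |

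The largest bias, 0.044, is 0.044/0.302 = 15% of the design difference.

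**Step 3: add waist.** Both biases go to zero and both rejection rates return to about 5%. Residual df falls from 54 to 53 (48 to 47 at N = 54). The standard error of the current hs-CRP slope changes by the factor √{(1 - r²)/[(1 - r²ρ²)(1 - ρ²)]}, which is 1.01 at r = -0.4, ρ = 0.4 and 1.11 at r = -0.3, ρ = 0.5.

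**The case against.** **The group comparison is largely protected already.** This stands. With current hs-CRP in the model, as planned, false rejection for the initial hs-CRP group is 5-8% at r = -0.3. A calculation that omits current hs-CRP overstates the problem for that comparison. The bias moves to the current hs-CRP coefficient, which bears on the second objective, so the point is narrowed but not removed.

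**Visit waist comes too late for the initial exposure.** This also stands. The initial evaluations date from 2006 to 2010, there is one study visit, and the synopsis puts the interval at 5 to 10 years. Waist at the visit may be a consequence of what happened after the initial hs-CRP, and change in adiposity is itself an objective. No section says that waist was recorded initially. The objection has less force for current hs-CRP, where exposure, waist and RHI come from the same visit.

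**A reader might infer that an hs-CRP association would be nothing but visceral fat.** The documents do not support that. They give no correlations. Under the assumptions above, the group bias is at most 15% of 0.302, and the smallest observed difference reaching p < 0.05 at 30 per group is about 1.96 × 0.2 × √(2/30) = 0.10. Abdominal fat may explain part of an association; nothing shows that it would explain all of it.

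**Waist is only a proxy, and the Mann-Whitney test takes no covariates.** Both are true. An imperfect proxy removes only part of the bias, so the return to 5% is the best case. The unadjusted test still relies on the BMI z-score matching alone.

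**Conclusion.** The point holds in limited form. BMI z-score is the sole adiposity control in both the matching and the model, the rationale names visceral fat, and waist is measured and unused. Part of an hs-CRP association with RHI may therefore reflect abdominal fat, mainly for current hs-CRP. Under the stated assumptions, the planned model falsely rejects for current hs-CRP in about 14-33% of studies and for the initial hs-CRP group in about 5-12%. These figures are illustrative: they rest on assumed correlations, linear relations, a waist component unrelated to the other covariates, and waist acting as a common cause. Weaker correlations would shrink them. They do not show that the group comparison is seriously compromised. They do show that the plan, as written, gives weak support to a claim that current inflammation acts independently of adiposity.

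**What to change.** 1. **Current hs-CRP objective.** Add visit waist-to-height ratio beside BMI z-score as a prespecified covariate. Report the hs-CRP estimate and its confidence interval with and without it.
2. **Initial hs-CRP group comparison.** Keep the planned covariates. Report the visit-waist adjustment only as a labelled sensitivity analysis, noting that visit waist follows the exposure by years and may lie on the pathway. Do not combine initial waist for some patients with visit waist for others.
3. **Same edit.** State whether the BMI z-score in the model is the initial or the current value.

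The cost is protocol wording, one degree of freedom and some collinearity between waist-to-height ratio and BMI z-score. That collinearity widens the intervals of those two coefficients; the interval for current hs-CRP widens by about 1-11% under the assumptions used. No new measurement is needed. The Mann-Whitney test is unchanged, and its report should say that adiposity is handled there only through the matching. The covariate should be fixed before the data are analysed, since adding it afterwards would look selective.

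### Sex is neither a matching factor nor a covariate in the RHI comparison, so a sex difference between the hs-CRP groups would go uncorrected

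*Combined protocol and SAP*

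**What the plan says.** The Recruitment section (Study population) selects 30 patients with raised initial hs-CRP and the same number without, the latter "matched for age, BMI z-score, and blood pressure". The Statistical methodology section compares RHI by a Mann-Whitney U test, which takes no covariates, and by what it calls a multivariate analysis of variance, "taking current hCRP, age, BMI z-score, and systolic blood pressure into account". Both lists are complete as written. Sex does not appear in either, nor as a stratum or an eligibility item.

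Under Study intervention, the overview of the visit adds that "a selfscore of pubertal development using standardized pictures will be done". Pubertal stage is not among the listed RHI covariates.

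The Overall design section calls the study an observational cohort, and the title asks whether low grade inflammation is an independent risk factor for endothelial dysfunction.

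**The concern.** Without randomisation, the claim of independence rests wholly on matching and adjustment. For the Mann-Whitney test, matching is the only protection, and sex is unmatched. The adjusted model does not make up for this, because sex is missing there too. A BMI z-score describes adiposity against a reference; having it in the model does not adjust RHI for sex. Age cannot stand in for sex either.

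If the raised hs-CRP group contained systematically more of one sex, and RHI differed by sex, part of the group difference would be a sex difference reported as an effect of inflammation. It could also mask a real effect, depending on direction. Under the plan as written, an effect called independent would not be independent of sex.

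**Working it through.** **Inputs from the documents**
- Mean and SD of RHI: "Assuming a mean RHI score of 1.51 in overweight children with a standard deviation of 0.2".
- Planned difference and group size: "we have a power of 0.80 to demonstrate a difference of 20 % between the two groups with 27 patients enrolled in each group". Read as relative, the difference is 0.20 × 1.51 = 0.302.
- Alpha 0.05; two-sided is assumed, because sidedness is not stated.
- Number studied: "In total 60 participants will be investigated", so 30 per group.

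**Inputs that are assumptions** (the documents give neither)
- Sex effect on RHI: 0.1 to 0.2 units, or 0.5 to 1 SD.
- Systematic sex imbalance between groups: 20 percentage points.

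**Step 1. The plan's own power figure.** The standard error at 27 per group is 0.2 × √(2/27) = 0.0544. Then 0.302 / 0.0544 = 5.55, and power = Φ(5.55 − 1.96) = 0.9998. The stated 0.80 does not reproduce; 27 per group gives 80% power for a difference of about 0.152 (10.1% of 1.51). That is a separate matter. What counts here is that power at the planned difference is above 0.999 before any covariate is added, so sex in the model has practically no power to gain there.

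**Step 2. Shift in the group difference.** Shift = imbalance × sex effect.
- 0.20 × 0.1 = 0.02, and 0.02 / 0.302 = 7%.
- 0.20 × 0.2 = 0.04, and 0.04 / 0.302 = 13%.

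**Step 3. Type I error of the unadjusted comparison.** This uses the normal approximation, 30 per group and SD 0.2. The standard error is 0.2 × √(2/30) = 0.0516. With k = shift / 0.0516, the error is 1 − Φ(1.96 − k) + Φ(−1.96 − k).
- Shift 0.02: k = 0.387, error = 0.067.
- Shift 0.04: k = 0.775, error = 0.121.

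Both values hold only if the imbalance is systematic, that is, if sex and hs-CRP group are associated.

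**Step 4. Chance imbalance alone.** With half girls assumed in each group of 30 and no link between sex and hs-CRP, the two counts of girls are independent Binomial(30, 0.5). The probability that they differ by 6 or more (20 points) is 0.155, both directions together. This does not inflate the type I error. Simulations of the Mann-Whitney test with random sex and a sex effect of 0.2 gave a rejection rate of 4.5% to 4.8% at a nominal 5%.

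**Step 5. How demanding the upper assumption is.** With equal sexes and a total SD of 0.2, a sex difference of 0.2 explains (0.2/2)² / 0.2² = 25% of the RHI variance; a difference of 0.1 explains (0.1/2)² / 0.2² = 6.25%. The upper end of the range is therefore a strong sex effect.

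**The case against.** The strongest reply is that nothing in the documents shows sex to be related to RHI or to hs-CRP. Without both links there is no confounding, and every effect size above is assumed. This stands as a limit on magnitude: the bias is potential and its size cannot be set from the documents. It does not answer the omission, since a study that claims an independent effect should be able to show that sex does not produce it.

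Three stronger readings are tempting, and the documents do not support them.

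- **A reader might infer that the 15.5% chance of a 20-point imbalance is itself a bias.** It is not. With no link between sex and hs-CRP, the standard error already covers chance imbalance, and the simulated error stays near 5%.
- **A reader might infer a useful gain in power.** At the stated 20% difference there is none to be had. A gain appears only against a smaller target, such as about 10%, which the protocol does not state, and with an assumed share of variance explained.
- **A reader might put puberty on the same footing as sex.** That case is weaker. Age is both matched and adjusted. The self-score is taken at the visit, after the initial hs-CRP. Initial evaluations were in 2006 to 2010 and the protocol is dated August 2018, at least about 7.6 years later, so a 12-year-old at the visit would have been about 4 at the initial work-up. Few participants are likely to be in early puberty. Nor can one say that the score serves no purpose, because the documents do not state its use. They support only that it is not a listed RHI covariate.

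It is also fair that the size of the control pool and the matching tolerances are not given, so a fourth matching factor may be harder to meet than it looks.

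**Conclusion.** The point holds as a gap in confounder control. Sex is in neither the matching nor the covariate list, so if it is related to both hs-CRP group and RHI, neither planned analysis removes the resulting bias. The omission is certain; its effect is unknown. The illustrated shift of 0.02 to 0.04 and type I error of 6.7% to 12.1% rest on an assumed systematic 20-point imbalance, an assumed sex effect of 0.1 to 0.2, 30 per group and SD 0.2. They are not properties established for this study. The case for change rests on possible bias, not on precision, and the correction is cheap enough to be worth making despite the uncertainty.

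**What to change.** Add sex as a pre-stated covariate in the adjusted RHI model. Where the pool of controls allows, also match controls on sex, which gives the unadjusted Mann-Whitney test some protection. The covariate is the more important of the two: matching is on initial hs-CRP status, so it does not secure balance for the objective that relates RHI to current hs-CRP.

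Optionally, add self-scored pubertal stage in a pre-stated sensitivity analysis only, because it is measured after the initial hs-CRP.

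Cost: one model degree of freedom. With 54 patients, an intercept, the group term and four covariates leave 54 − 6 = 48 residual degrees of freedom; sex makes it 47. Matching becomes somewhat harder, by an amount that cannot be judged without the pool size. The documents do not name sex as a collected item, but it should be available from the medical file. Make both changes before controls are selected and data are seen: matching cannot be added afterwards, and a covariate added late invites a charge of selective analysis.
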